To effectively address the Primary and Secondary Objectives of this interventional study, we will enroll subjects, age 3 through 16 years, either sex, any race, any ethnicity with a serum IgE [UniCAPTM] to egg of \geq 5 kU_A/L [determined by UniCAPTM within the past 12 months]. All subjects will have documented consent and assent as is appropriate. Females of childbearing age will use appropriate birth control. These subjects will be recruited from 5 sites. All eligible subjects will receive the double-blind placebo controlled baked egg OFC. Approximately the first 40 individuals who do not pass this initial baked egg food challenge will be assigned to Egg OIT. Enrollment in this group will be capped at approximately 40 individuals though those consented but not yet challenged when this group reaches 40 will be allowed to proceed and if they fail the baked egg challenge will be assigned to the egg OIT assignment group. This may result in slightly over 40 cases in this group which is acceptable. Individuals who pass the baked egg OFC will then have an initial egg OFC. Those who have dose-limiting symptoms at a cumulative dose of \leq 1444 mg egg white protein will be randomized 1:1 to Baked Egg or Egg OIT. Those who successfully consume more than 1444 mg of egg white protein on the OFC will not be eligible for the study and will be followed per local standard of care.

Those assigned or randomized to Egg OIT will escalate the dose of egg white solid to achieve the desired maintenance dose of 2500 mg. Those randomized to the Baked Egg group will continue on the baked egg product for the remainder of the study.

Throughout this protocol, the doses of egg white solid for Egg OIT are given in milligrams of egg white solid, not egg white protein. It is estimated that 1 mg egg white solid is equivalent to approximately 0.70 mg of egg white protein.

A schematic is presented below:

For the purposes of this study, clinical details and blood samples will be collected at specified intervals. If a subject is removed from therapy because of failing escalation or build-up, a blood sample for mechanistic studies will be obtained within approximately 1 week of removal from therapy.

Subjects will have an annual phone follow-up at 1, 2 and 3 years after completing the active portion of the study through September 30, 2018.

The Baked Egg Group

The Baked Egg group will use approximately 2 gm of baked egg as a daily dose throughout the study as described below.

Baked Egg therapy will consist of a muffin or equivalent (1/3 of egg in serving, approximately 2 gm).

Home baked products will have no more than 2 eggs per batch of recipe (yield 6 servings). Serving size is indicated by the yield of the recipe. Products will be baked for 25-50 minutes at 325-425 degrees Fahrenheit. Recipes will be provided. The daily dose can be administered at a single sitting or divided throughout the dosing day. Adjustments in the daily dosing may be made at the investigators discretion based on symptoms experienced by the subjects in the baked egg group.

Dietary information will be provided to the subject regarding allowed consumption of various commercial foods consistent with approximately 2 gm of baked egg per daily dose. Subjects in this arm will be encouraged to ingest "safe" commercial products in addition to their daily 2 gm intake of baked egg protein. These foods will be recorded on the daily logs.

The Egg OIT Group

The Egg OIT treatment consists of 2 groups that may experience different paths for OIT treatment. The group that fails the baked egg challenge may be more sensitive to egg dosing, and may experience more reactivity and adverse reactions. These subjects will stop at 12 mg egg white solid on the initial day escalation and thereby have a slightly slower escalation time course.

The Egg OIT treatment is comprised of an initial escalation day, an initial build-up phase to last a maximum of 44 weeks, and followed by at least 8 weeks of daily therapy at the maximum achieved dose (350 mg - 2500 mg egg white solid).

Initial Day Escalation Schedule					
Dose no.	Egg white solid dos	e (mg) Cumulative Egg dose (mg)*			
1	0.1 mg	0.1 mg			
2	0.2 mg	0.3 mg			
3	0.4 mg`	0.7 mg			
4	0.8 mg	1.5 mg			
5	1.5 mg	3.0 mg			
6	3.0 mg	6.0 mg			
7	6.0 mg	12 mg			
8	12 mg	24 mg			
9	25 mg	49 mg			
* If no de-e	escalation	_			

Dosing Schedule for Egg OIT

Frequency standard every 30 min

Subjects at the end of the first day, tolerating less than 3 mg single dose, will be considered an initial day escalation desensitization failure. *The Egg OIT assignment group (that failed the Baked Egg challenge) will only escalate to 12 mg maximum on Day 1.*

Subjects tolerating only 3, 6 or 12 mg single dose will go home on the greatest tolerated dose to be given daily (first dose given in Clinical Research Center under observation). All escalations will occur no sooner than 2 weeks and single dose increases in the Clinical Research Center from 3 to 6 to 12 to 25 mg will be attempted. These doses will be weighed doses in individual vials until the maximum 25 mg dose is reached.

All subjects will return on Day 2 and receive their maximum tolerated dose under direct observation.

Subjects with moderate symptoms observed on Day 2 will return on Day 3 for the next lower dose under observation in the Clinical Research Center or monitored clinic setting.

Doses on Day 2, 3, and 4 must be at least 3 mg or the subject will be considered an escalation failure.

Dose #	Dose egg white solid	Dose Method	Interval (weeks)	% Increase
8	12 mg	Vial	2	
9	25 mg	Vial	2	108%
10	50 mg	capsule*	2	100%
11	75 mg	capsule	2	50%
12	100 mg	capsule	2	33%
13	150 mg	capsule	2	50%
14	225 mg	capsule	2	50%
15	260 mg	scoop 0 [†]	2	15%
16	350 mg	scoop 1	2	35%
17	450 mg	scoop 2	2	30%
18	550 mg	scoop 3	2	20%
19	700 mg	scoop 4	2	25%
20	830 mg	scoop 5	2	20%
21	1100 mg	scoop 6	2	30%
22	1320 mg	scoop 7	2	20%
23	1720 mg	scoop 8	2	30%
24	2130 mg	scoop 9	2	25%
25	2500 mg	scoop 10	2	15%

All scoops are approximate weights based on scoop size and leveling.

Those subjects who achieved a dose of 2500 mg egg white solid during the initial build-up period will continue maintenance therapy for up to 12 months after the 1 year 7444 mg egg white protein OFC. Those subjects who achieved less than 2500 mg during the initial buildup phase will be escalated from their maintenance dose (pre-1-year 7444 mg egg white protein OFC) up to 2500 mg, if tolerated, following the same escalation time table from the initial build-up phase. No dose escalation will be performed within 1 month of a subject's planned 2 year 7444 mg egg white protein OFC.

Follow-up OFCs

At 1 year:

A 7444 mg egg white protein OFC will be performed at 1 year to identify desensitized individuals.

At 2 years:

Those subjects still on active treatment (Baked Egg or Egg OIT) will have a 7444 mg egg white protein OFC on therapy at 2 years. Those subjects still on active therapy, but escalating doses, will discontinue escalation for 1 month prior to their 2 year 7444 mg egg white protein OFC and will be maintained on their highest tolerated dose. Those who pass the 2 year egg 7444 mg egg white protein OFC on therapy will have a repeat 7444 mg egg white protein OFC after 8-10

weeks off therapy to test for sustained unresponsiveness. If they pass this OFC off therapy (including open feeding), they will add egg to their diet and will be followed at 3 months by phone and at 6 months in clinic to assess their egg diet history and reactivity status to egg. They will be contacted annually for additional phone follow-up through September 30, 2018.

If they fail the 2 year 7444 mg egg white protein OFC on or off therapy, they will stop therapy and the study physician will review treatment options. They will also be contacted annually for additional phone follow-up through September 30, 2018.

Mechanistic Laboratory Assessments

Mechanistic labs are obtained at screening (Visit 00), 3 month (Visit 02), 6 month (Visit 03), 1 year (Visit 04), 16 months (Visit 05), 20 months (Visit 06), the 2 year visit (Visit 07), and at the 2 year sustained unresponsiveness visit (Visit 08), if applicable.

Study Design Safety Considerations

The design considers important safety issues:

- All dose escalations will be supervised in the clinic.
- The Egg OIT assignment group (that failed the baked egg challenge) will only escalate to 12 mg egg white solid maximum during the initial escalation on Day 1.
- OFC can delineate individuals who can ingest egg safely in a supervised setting.⁷⁹
- The relationship of egg-specific IgE to OFC results is unknown in individuals consuming baked egg or 350 2500 mg of egg white solid daily for up to a year. Thus, after long-term therapy, an egg OFC will be needed to determine sustained unresponsiveness irrespective of their egg-specific IgE level, and this will be performed safely in a supervised setting.

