Endpoints and analysis: Serious adverse event rates and types of events will be compared between those receiving Egg OIT and those receiving Baked Egg.

Expected outcome/potential limitations: Comparing serious adverse event rates will serve as a measure of safety in implementing Egg OIT vs. Baked Egg as a therapy for food allergy. This comparison may be limited by the small sample size. It may also be limited if serious adverse events occur rarely. However, if serious adverse events occur rarely in both arms, it would support the safety of the therapy as administered in this protocol and not preclude further clinical investigation.

3. Characterize unrestricted egg consumption after conclusion of treatment via long term followup

Rationale: The durability of sustained unresponsiveness following Egg OIT is currently unknown. Previous studies in other foods have indicated a return to reactivity without continued consumption while results from the prior Egg OIT trial indicate that treatment effect may be durable. Following subjects longitudinally to assess diet and frequency of consumption will aid in understanding the long term impact of Egg OIT.

Overview of methods: Subjects will be contacted annually through September 2018 to complete a phone questionnaire assessing diet and frequency of consumption. Questionnaires will be completed based on time from randomization.

Endpoints and analysis: The endpoint of interest is unrestricted consumption of egg in the diet. Other endpoints including frequency of consumption and any reactions will also be solicited. The analysis will be primarily descriptive with rates of unrestricted consumption described by treatment group and final study status. Numbers permitting, formal comparisons between treatment groups may be performed similar to the primary analysis.

Expected outcome/potential limitations: The number of subjects consenting to be followed longitudinally after two years of treatment may be lower than anticipated. Further, the questionnaire is self-report and likely will be subject to recall bias. As the purpose of this analysis is primarily descriptive these are considered acceptable limitations.

Tertiary Objectives - Mechanistic:

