9.3 Sample Size and Power Calculations

The sample size target for the randomized portion of the study is 96 individuals with 1:1 random assignment to Baked Egg and Egg OIT. The sample size was selected to determine whether a

difference exists between the treatment groups in the primary endpoint rate for the sustained unresponsiveness-focused portion of the study. Specifically, the sample was designed to have 85% power to detect with a two-sided 5% level test, a difference between a 40% and 70% sustained unresponsiveness rate. While a small dropout rate may occur, we will use all randomized cases who initiate treatment in the intent-to-treat analysis of the primary endpoint; failures associated with noncompliance are include in the denominator for event rates above.

This sample size is sufficient to address the secondary endpoint of the desensitization components of the study for event rate differences of comparable size.

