9.4 The Egg OIT assignment group who failed the initial baked egg challenge

The subset of individuals who are not baked egg tolerant at baseline comprise a selected group of individuals where Egg OIT will be examined. The size of the group will be capped at approximately 40 subjects. The study cohort should be useful for both clinical and mechanistic study with approximately 40 such individuals enrolled. The 2 year sustained unresponsiveness rate will be compared to historical experience as well as the protocol's randomized Egg OIT arm. Mechanistic studies will be examined to determine if baseline immune system responses are similar in both Egg OIT groups. Immune parameter changes will be examined to determine if tolerant and non-tolerant cases have response profiles that are parallel for the 2 strata.

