9.2 Deaths, Serious Adverse Events and other Significant Adverse Events

The proportion of participants experiencing a SAE will be estimated within each group. Pairwise comparisons between treatment groups will be performed using Barnard's exact unconditional test at the two-sided 5% level. If multiple SAEs are observed within a participant, alternate methods to account for the multiple events will be considered. If SAEs are infrequent (e.g. 1 or 2 events throughout the study), then hypothesis testing may not be performed. SAEs will also be described by relatedness to study product or procedure.

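### Few SAEs are to be read as support for safety, but no confidence bound on SAE risk is required; 0 of 48 children still allows a true risk of 7.4%

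*Protocol*

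**What the plan says.** Protocol 2.1, Secondary Objective 2, compares SAE rates between Egg OIT and Baked Egg. Under expected outcome and limitations it warns that "This comparison may be limited by the small sample size" and adds that rarity may also limit it. The next sentence then says that "if serious adverse events occur rarely in both arms, it would support the safety of the therapy as administered in this protocol", and that further clinical study would not be ruled out. No number is attached to *rarely*.

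SAP 9.2 gives the analysis:
- On estimation: "The proportion of participants experiencing a SAE will be estimated within each group".
- On testing, the groups are set against each other two at a time with a Barnard test, two-sided at 5%.
- On very low counts: "If SAEs are infrequent (e.g. 1 or 2 events throughout the study), then hypothesis testing may not be performed".

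SAP 6.1 adds only frequencies and percentages for categorical measures. CI is in the SAP's abbreviation list, but neither 6.1 nor 9.2 calls for one. SAE incidence is the pre-defined secondary safety endpoint (SAP 3.3), and SAP 9 calls it the primary safety endpoint.

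**The concern.** The protocol draws a favourable conclusion in the very case where it says the data are weak. A low count in a small arm is weak evidence of a low risk, and how weak can be stated exactly with an upper confidence limit. The plan does not ask for that limit. If the test is run, the output is a proportion and a p-value. If it is not run, the output is a proportion alone. Either way the report could state that rare SAEs support safety without showing the largest SAE risk the data still allow. In a trial that doses allergic children with the allergen, readers need that figure.

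**Working it through.** **Inputs**
- Randomised: "The sample size target for the randomized portion of the study is 96 individuals with 1:1 random assignment to Baked Egg and Egg OIT" (Protocol 9.3), so 96/2 = 48 per arm.
- Assigned Egg OIT group: "The size of the group will be capped at approximately 40 subjects" (Protocol 9.4). All Egg OIT is then about 48 + 40 = 88, and all treated about 96 + 40 = 136.
- Test: Barnard, two-sided 5% (SAP 9.2).
- Expected SAE rate, or SAE rate to be excluded: none stated in either document.

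**1. The plan's own figure.** Protocol 9.3 claims "85% power to detect with a two-sided 5% level test, a difference between a 40% and 70% sustained unresponsiveness rate". With the pooled formula, n = [1.960·√(2·0.55·0.45) + 1.036·√(0.4·0.6 + 0.7·0.3)]² / 0.30² = (1.379 + 0.695)² / 0.09 = 47.8, so 48 per arm. Power at 48 is 85.1% by formula and 85.4% by exact enumeration. The figure reproduces, but it concerns sustained unresponsiveness. Nothing was sized for SAEs.

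**2. What a low SAE count excludes.** The upper limit of the two-sided exact (Clopper-Pearson) 95% interval for x of n is the 0.975 quantile of Beta(x+1, n−x). For x = 0 it is 1 − 0.025^(1/n); for example 1 − 0.025^(1/48) = 7.4%.

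| Group | n | 0 SAEs | 1 SAE | 2 SAEs |
|---|---|---|---|---|
| One randomised arm | 48 | 7.4% | 11.1% | 14.3% |
| Assigned Egg OIT | 40 | 8.8% | 13.2% | 16.9% |
| All Egg OIT | 88 | 4.1% | 6.2% | 8.0% |

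These limits need no assumed SAE rate.

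**3. What the test adds.** Barnard p-values at 48 per arm, with no SAEs in the other arm:

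| SAEs | 1 vs 0 | 2 vs 0 | 3 vs 0 | 4 vs 0 |
|---|---|---|---|---|
| p | 0.53 | 0.21 | 0.092 | 0.049 |

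Rejection first occurs at 4 vs 0. As an illustration, assume true risks of 4% and 0%. Power is then P(X ≥ 4 | 48, 0.04) = 1 − (0.699 + 0.176) = 12.5%, where 0.699 = P(X ≤ 2) and 0.176 = P(X = 3).

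**4. How often the no-test case would arise at an assumed 4%.** P(X ≤ 2) = Σ C(n,k)·0.04^k·0.96^(n−k), k = 0 to 2:
- One randomised arm affected, no SAEs elsewhere (n = 48): 70%. Counting the two randomised arms only, a background risk of 1% or 2% in the other arm lowers this to 57% or 45%.
- All Egg OIT children affected, no SAEs in Baked Egg (n = 88): 31%.
- Both randomised arms affected, no SAEs in the assigned group (n = 96): 26%.
- All children affected (n = 136): 9%.

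**5. The enrollment-suspension rule at the same assumed 4%,** if every SAE were therapy-related. P(X ≥ 2) is 58% (n = 48), 87% (88), 90% (96) and 97% (136).

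**The case against.** The case for leaving the plan alone has five parts.

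- **The protocol's language is modest.** It discloses the limitation, speaks of support rather than proof, and frames the result as not blocking further study. That is fair, but the disclosed limitation is set aside in the next sentence and no bound is put in its place.
- **Omitting the test costs nothing.** This stands. The clause is permissive, and with two or fewer SAEs the randomised comparison cannot reject. The gap is that no interval is required in either branch.
- **Other safeguards exist.** Protocol 3.3 suspends enrollment pending DSMB review after more than one serious suspected adverse reaction, and therapy-caused SAEs would often trigger it (step 5). That rule covers related events only, acts on enrollment, and does not govern what the final report may conclude about SAEs.
- **Safety does not rest on SAEs alone.** SAP 9.1.1 compares dosing symptoms and describes moderate and severe reactions and epinephrine use. These are valuable, but the sentence in Protocol 2.1 is about SAEs.
- **A reader can compute the limit, or the table shells may show it.** Both are possible. SAP 16 places the shells in a separate document, and the plan should not depend on either.

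A reader might go further and infer that a therapy causing SAEs in 1 in 25 children would usually be read as safe. The documents do not support that. They give no SAE rate. The SAP's condition counts events across the whole study, and *usually* (70%) needs the 4% confined to one arm of 48 with no SAEs elsewhere. If all Egg OIT children, both randomised arms or all children are affected, the chance is 31%, 26% or 9%. Nor do the documents say that a non-significant test shows safety.

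**Conclusion.** The concern holds as a gap in inference and reporting. The protocol lets rare SAEs stand as support for safety without defining rare, and the SAP requires no bound on SAE risk whether or not the test is run. At the planned sizes, even zero SAEs leaves a risk of up to 7.4% in a randomised arm, 8.8% in the assigned group and 4.1% in all Egg OIT children combined.

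The limits assume full accrual (48, 48 and about 40), independent children, and an SAE outcome counted as children with at least one event. SAP 6.3 restricts the safety population to treated participants, so any untreated child widens them slightly. Whether 7.4% is tolerable is a clinical question that the documents do not address. The primary endpoint and trial conduct are unaffected, so this is a cheap improvement rather than a fault that threatens the trial.

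**What to change.** **SAP 9.2.** Whatever the number of SAEs, and whether or not a test is run:
- Report the proportion of children with an SAE and its exact (Clopper-Pearson) 95% interval for Baked Egg, eOIT-Randomized and eOIT-Assigned, and for all Egg OIT children combined. The combined figure supplements the separate ones, because the two Egg OIT groups differ in baked-egg tolerance.
- Report the risk difference with a 95% interval (unconditional exact or Miettinen-Nurminen) for each pairwise contrast.

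**Protocol 2.1, Secondary Objective 2.** Replace the sentence on rare SAEs with a statement that few SAEs will be reported as excluding only risks above the upper 95% limit, for example 7.4% if 0 of 48.

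**Cost.** A few lines in the SAP and one sentence in the protocol, with no new data. The safety statement becomes slightly less favourable.

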3.1 Primary Efficacy Outcome Measure

The primary clinical efficacy end-point is the development of sustained unresponsiveness to egg consumption at 2 years as assessed with a 7444 mg egg white protein OFC and open feeding, 8-10 weeks after discontinuing therapy.

3.2 Secondary Endpoints

The secondary outcome measures are as follows:

- The development of desensitization to >4444 mg egg white protein at 1 year and 2 years.
- Incidence of all serious adverse events during the study.
- Unrestricted consumption of unbaked egg as reported on the annual long term questionnaire
- Changes in egg-specific IgE and IgG4, changes in PST mean wheal diameters, basophil reactivity, CD154+ CD4+ Th2 cells, Tregs, and Tfh cells as described in Section 2.1.

3.3 Criteria for Premature Termination of the Study: Stopping Rules

Study enrollment will be suspended pending expedited review of all pertinent data by the NIAID DSMB if the following occurs:

• Any death related to Baked Egg or Egg OIT dosing.
- More than 1 severe anaphylactic reaction (see Appendix 3) related to Baked Egg or Egg OIT dosing at any stage of the protocol.
- More than 3 treatment-related non-anaphylaxis severe adverse events (including EoE).
- More than 1 serious suspected adverse reaction occurs (serious and related).
- More than 3 subjects who require more than 1 injection of epinephrine for a single study product related allergic reaction during the study therapy.

4. Selection and Withdrawal of Subjects

